## 8.5 Study population with inclusion and exclusion criteria

The source population will comprise all females aged >10 present in the database at any time during the period from  $1^{st}$  of January 2010 (or start according to the database) to end of data availability. All patients will need to have at least 365 days of data visibility prior to index date.

For patient-level DUS, the study population will be additionally restricted to new medicine users (see "8.6. Variables" for further details). For objective 2, 4 and 5 these will be restricted to participants newly

 $^{2}$  Indicating whether patients are allowed to enter the study population only once or multiple times

<sup>3 IP = inpatient, OP = outpatient

<sup>4 RxNorm codes will be identified based on ATC codes.

P3-	C3-0	206	Study	/ Pro	tocol

Version: V4.0

Dissemination level: Public

prescribed with NOMAC or CMA. For objective 3, these will be all drug classes of interest. A preliminary list of concepts for meningioma can be found in **Appendix I**.

Further information on exposures can be found in see "8.6.1. Exposures". The operational definitions of the inclusion and exclusion criteria are presented by means of **Table 5** and **Table 6**, respectively.

**Table 5.** Operational definitions of inclusion criteria.

Criterion	Details	Order of application 	Assessment window	Care Settings 	Code Type	Diagnosis position 	Applied to study populations:
Observation period during the study period	All individuals present after the study start date	N/A	N/A	IP, OP	N/A	N/A	All
Sex	Females only	N/A	N/A	IP, OP	N/A	N/A	All
Age	Individuals aged >10	Before	N/A	IP, OP	N/A	N/A	All
History of meningioma	Individuals with prior history of meningioma	Before	[-Inf, -1]	IP, OP	SNOME D	Any	Patients with prior history of meningioma (objective 1, subgroup analysis)

<sup>1 Relative to the study entry date

**Table 6.** Operational definitions of exclusion criteria.

Criterion	Details	Order of application	Assessment window	Care Settings 	Code Type	Diagnosis position 	Applied to study populations:
Prior database history	Study participants with less than 365 days of prior history observed at index date will be excluded	Before	[-365, -1]	IP, OP	N/A	N/A	General population (objective 1 and 6)
Prior database history	Study participants with less than 365 days of prior history observed at index date will be excluded	After	[-365, -1]	IP, OP	N/A	N/A	All except general population (objective 1 and 6)
Prior use of NOMAC	Individuals with prior prescriptions of NOMAC will be excluded	After	[-Inf, -1]	IP, OP	N/A	N/A	New users of NOMAC (objective 2, 4 and 5)
Prior use of CMA	Individuals with prior prescriptions of CMA will be excluded	After	[-Inf, -1]	IP, OP	N/A	N/A	New users of CMA (objective 2, 4 and 5)

<sup>2 IP = inpatient, OP = outpatient

<sup>3 Specify whether a diagnosis code is required to be in the primary position (main reason for encounter)

Authors: [name], [name], [name], [name], [name]

Version: V4.0

**Dissemination level:** Public

Prior use of	Individuals with prior	After	[-Inf, -1]	IP, OP	N/A	N/A	New users of
drug classes	prescriptions of any of the						drug classes
of interest	drug classes of interest will be						or
(any)	excluded						progestogens
							of interest
							(objective 3)

<sup>1 Relative to the study entry date

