In July 2022, PRAC issued further recommendations for both NOMAC and CMA. PRAC recommended to update the summary of product characteristics for products containing NOMAC or CMA to inform of the risk of meningioma. PRAC recommended that medicines containing high-dose chlormadinone (5 – 10 mg) or high-dose NOMAC (3.75 – 5 mg) should be used at the lowest effective dose and for the shortest duration possible. These medications should only be used when other interventions are not appropriate and should no longer be considered for first-line treatment. Similar to what was already established for NOMAC, treatment with products containing NOMAC or CMA was contraindicated in patients with current or prior history of meningioma. PRAC also recommended monitoring patients for symptoms, and permanently discontinuing treatment if the patients develop meningioma. (9) Measures recommended by PRAC were endorsed by the Committee for Medicinal Products for Human Use (CHMP) and the European Commission issued final legally binding decisions applicable in all the European Union (EU) Member States, between 28th of October and 28th November 2022.(10) Following this decision, a direct healthcare professional communication (DHPC) was sent to prescribers (8th November 2022)(11) and Marketing Authorisation Holders (MAH) had one month to implement changes (28th December 2022). Dates for national-level interventions varied, especially in the case of France, where additional interventions were put in place between 2018 and 2021.

The overall aim of the study is to describe how prescribing of NOMAC and CMA has changed following the introduction of risk minimisation measures (RMM) in November 2022. To contextualise findings, it is also of interest to study changes in prescribing of other relevant drug classes, including progestogen and oestrogen combination products and progestogens that are pregnadien derivatives, and to study the impact of prior EU-level restrictions in trends of NOMAC prescribing.

D2 C	2 000	Charles	Donate and
P3-C.	3-UU6	Stuav	Protocol

Version: V4.0

**Dissemination level:** Public

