## 8.4 Follow-up

For the population-level DUS (objective 1), study participants in the denominator population will start contributing person time on the latest of the following: 1) study start date (1st January 2010, or as defined according to the database), 2) date on which they turn 10 years old, 3) date at which they have a year of prior history recorded. Participants will stop contributing person time at the earliest date of the following: 1) end of available data in each of the data sources, 2) date at which their observation period ends (e.g. loss to follow-up, death).

For the patient-level DUS (objective 2 to 5), participants will be followed up from the day of incident prescription of medication (index date), until the earliest end of data availability, date at which their observation period ends (e.g. loss to follow-up, death), or 180 days after ending treatment (objective 5). For objective 2, 4 and 5, index date will be defined as the date of the first-ever prescription of NOMAC or CMA. For objective 3, this will be defined as the date of the first-ever prescription of any of the 6 drug classes of interest (see "8.6.2 Outcomes").

For objective 4, line of treatment will be assessed retrospectively by looking at prior records of alternative treatments, from the date of initiation of treatment with products containing NOMAC or CMA to start of the study period (1st January 2010, or as defined according to the database).

For objective 6, follow-up will be the same as that for objective 1.

Information on the operational definition of index date is described in **Table 4**. Please note that, for objectives 1 and 6, each drug class of interest will be assessed separately, with the washout window specific to the drug class being studied (e.g., when studying NOMAC, the washout window will be applied with respect to this substance only). For objective 3, the washout will be applied to all the drug classes of interest combined.

Authors: [name], [name], [name], [name], [name]

Version: V4.0

**Dissemination level:** Public

Table 4. Operational definition of time 0 (index date) and other primary time anchors.

Study population names	Time Anchor Description (e.g. time 0) 	Number of entries 	Type of entry	Washout window	Care Setting 	Code Type 	Incident with respect to

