#### **Covariates for stratification:**

Covariates for stratification will vary across objectives and will include:

- Age group:
   10-17, 18-34, 35-49, 50-64, +65 years.
- Indication:

Non-HRT vs. HRT. Indication will be assessed using age as a proxy (non-HRT in women aged 10-49 years, HRT in women aged >50 years).

- Dose:
  - High- vs low- dose, for NOMAC or CMA only. For NOMAC, high doses will include amounts from 3.75mg to 5mg. For CMA, high doses will include amounts from 5mg to 10mg. Low doses will be any amounts less than those specified.
- WHO 5th ATC level codes:
  - For NOMAC or CMA only, if counts allow. For NOMAC codes included will be: G03AA14, G03DB04, G03FB12. For CMA, codes included will be: G03AA15, G03AB07, G03DB06, G03FB03.
- Time period:
  - Preintervention: from start date to October 2022; Postintervention: from February 2023 to study end.

See below which covariates apply according to each objective.

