#### Objective 4:

For each participant initiating treatment with NOMAC or CMA, we will retrospectively assess the occurrence of records indicating the use of other drug classes of interest not containing NOMAC or CMA. This assessment will be performed from the day before index date to the earliest of the start of the study period or the start of the observation period for each patient. We will describe the order in which treatments of interest were prescribed, as first vs. non-first treatments. NOMAC and CMA will be assessed separately.

NOMAC and CMA will be assessed separately. Results will be reported overall and stratified by study period (pre- vs. postintervention), dose (high- vs. low-dose products), and indication (non-HRT vs. HRT). Dose and indication will be assessed at index date (i.e. date of treatment initiation with NOMAC or CMA). Please see "11. Limitations" for more information.

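### In Objective 4, and in the Objective 3 dose counts, a high-dose start that follows low-dose use of the same substance is not counted as a high-dose start

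*Protocol*

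**What the plan says.** Section 6 of the protocol describes the 2022 measure for high-dose products: "These medications should only be used when other interventions are not appropriate and should no longer be considered for first-line treatment". Section 8.6.3 defines high dose: "For NOMAC, high doses will include amounts from 3.75mg to 5mg" and "For CMA, high doses will include amounts from 5mg to 10mg". It lists dose as a stratification covariate for Objectives 1, 4 and 6.

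For Objectives 2, 4 and 5, Section 8.4 sets the anchor: "index date will be defined as the date of the first-ever prescription of NOMAC or CMA". Table 4 allows a single entry. Table 6 adds "Individuals with prior prescriptions of NOMAC will be excluded" and "Individuals with prior prescriptions of CMA will be excluded", both with an unlimited lookback window and neither mentioning dose. For Objective 4, Section 8.8 states "Dose and indication will be assessed at index date (i.e. date of treatment initiation with NOMAC or CMA", and it counts as an earlier line only products that contain neither NOMAC nor CMA.

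For Objective 3, Section 8.4 applies the washout to all classes of interest together, and Section 8.8 reports how many patients start high or low doses.

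For Objectives 1 and 6, Section 8.8 sets a washout of 365 days after each treatment episode and lets women re-enter afterwards. On its level, Section 8.4 gives the example that, for NOMAC, "the washout window will be applied with respect to this substance only".

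**The concern.** Section 6 says these substances are used at lower doses for contraception and otherwise for gynaecological disorders and HRT. A woman may therefore have a low-dose product first and a high-dose product of the same substance later. Her high-dose start is one of the prescribing decisions that the measure addresses. If the cohort rules keep it out of the high-dose stratum, that stratum describes only women whose first recorded use of the substance was already high-dose. A before-and-after comparison of line of treatment in that stratum would then say nothing about the other high-dose starters. The limitations in Section 11 discuss changing indications and incomplete early data, but not this sequence.

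**Working it through.** The protocol has no figure to reproduce here, because the point concerns a cohort rule. The check has two steps.

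**Step 1: trace one woman through the rules.** She has recorded low-dose CMA (or NOMAC) first and high-dose use of the same substance later.

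| Objective | Rule | Her high-dose start |
|---|---|---|
| 4 | Single entry at first prescription of the substance; dose read at index | Not counted; she is in the low-dose stratum |
| 3 | Single entry at first use of any class of interest | Not counted among high-dose initiators |
| 2 | Same entry as Objective 4; no dose stratum | Later course still adds to cumulative dose |
| 5 | Period comparison also takes prevalent users | She can appear as a prevalent user |
| 1 and 6 | 365-day washout, re-entry allowed | Counted if it comes after the 365 days; otherwise lost, if the substance-level washout also governs the dose strata |

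There is one exception for Objectives 3 and 4. Only 365 days of prior data are guaranteed. If her low-dose use predates the recorded data, and for Objective 3 no other class of interest is recorded either, she is counted as a high-dose starter.

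**Step 2: what can be said about size.** Let p be the share of all high-dose starts that follow recorded low-dose use of the same substance. The Objective 4 high-dose stratum then holds 1 − p of them. The protocol gives no value for p, so these are assumptions: p = 10%, 30%, 50% gives 90%, 70%, 50%.

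For the first-line share, let f be the true share among all high-dose starts and g the share among the omitted ones. Then

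observed share = (f − p·g) / (1 − p).

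With f = 50% and p = 20% (both assumed):

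- g = 0: 0.50 / 0.80 = 62.5%, too high.
- g = 50%: (0.50 − 0.10) / 0.80 = 50.0%, no distortion.
- g = 60%: (0.50 − 0.12) / 0.80 = 47.5%, too low.

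The value g = 0 requires that earlier low-dose use of the substance count as a line. Under the protocol's definition it does not, so an omitted woman whose only earlier use was low-dose CMA or NOMAC would be labelled first-line, and g can be well above 0.

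The before-and-after change is no more predictable. Take a true fall from 50% to 40% and, for simplicity, g = 0. The SMD uses the usual formula for two proportions (assumed, as the protocol gives none): the difference divided by √[(p₁q₁ + p₂q₂)/2], where p₁ and p₂ are the two first-line shares and q = 1 − p. The true SMD is 0.10 / √[(0.25 + 0.24)/2] = 0.20.

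| p before → after | Observed share | Fall (points) | SMD |
|---|---|---|---|
| 20% → 30% | 0.50/0.80 = 62.5% → 0.40/0.70 = 57.1% | 5.4 | 0.11 |
| 20% → 20% | 62.5% → 0.40/0.80 = 50.0% | 12.5 | 0.25 |
| 30% → 20% | 0.50/0.70 = 71.4% → 50.0% | 21.4 | 0.45 |

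The same true fall is understated in the first row and overstated in the other two.

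**The case against.** Entry by substance is a coherent choice, applied consistently in Sections 8.4 to 8.6, and Objective 4 is worded for users of NOMAC or CMA products as a whole. Its hypothesis in Table 11 is a substance-level number of first-line starters, which dose-specific entry would not change. Later high-dose use also reaches Objective 2 through cumulative dose and, in part, Objective 5 through prevalent users. All of this stands for the overall results. It does not repair the high-dose stratum of Objective 4, because no other objective reports line of treatment by dose.

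A reader might infer three stronger claims that the protocol does not support:

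- *Such a woman is never counted as a high-dose starter.* This fails for Objectives 1 and 6, where women re-enter after 365 days.
- *The high-dose first-line share is inflated and the expected shift is hidden.* Inflation needs g below f, and the 62.5% above needs g = 0, which contradicts the protocol's own definition of a line. In the g = 0 illustration, attenuation further needs p to rise between the periods; with constant p the fall is exaggerated.
- *The high-dose interrupted time series undercounts.* The example in Section 8.4 explains that use of other classes does not trigger the washout. Section 8.8 does not say whether the dose strata have their own washout, so the loss is conditional.

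**Conclusion.** The point holds for the dose strata of Objective 4 and for the Objective 3 count of high-dose initiators. A high-dose start after recorded low-dose use of the same substance is absent from both, by rules fixed in the protocol's own tables and text. The Objective 4 high-dose result therefore covers only women whose first recorded use of the substance was high-dose, although the not-first-line measure concerns high-dose products without that limit.

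How many starts are missing is unknown, as is the direction of the effect on the first-line share and the SMD. The percentages above illustrate this and are not estimates. The direction turns on whether earlier low-dose NOMAC or CMA counts as a line, and the protocol currently says that it does not. By the same definition, a woman who moves from low-dose NOMAC to high-dose CMA with no other class recorded is labelled first-line.

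For Objectives 1 and 6 the loss is limited to high-dose starts during a low-dose episode or within 365 days of its end, and arises only if the substance-level washout is used in the dose strata. This is a worthwhile and inexpensive improvement. It does not undermine the substance-level results.

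**What to change.** - **Objective 4, high-dose stratum:** add to Tables 4, 6 and 7 a new-user cohort for high-dose NOMAC and one for high-dose CMA, using the dose ranges already in Section 8.6.3. Set the index at the first high-dose prescription and apply the washout to the high-dose product only.
- **Line-of-treatment table:** show prior low-dose NOMAC or CMA use as its own row. The first-line share can then be read with or without it as an earlier line.
- **Objectives 1 and 6, high-dose series:** apply the 365-day washout to the high-dose product, and say so in Section 8.4.
- **Overall results:** keep the substance-level cohorts as they are.

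The cost is two further cohorts, built from the concept sets already needed for dose stratification. The drawback is that a woman can appear in both dose strata, so the strata no longer sum to the overall count. A table footnote should say so.

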#### 8.6 Variables

Drug classes of interest will be identified based on Anatomical Therapeutic Chemical (ATC) codes, and will include:

- Progestogens and oestrogens combinations
- Progestogens that are pregnadien derivates

Progestogens of interest (some included in the groups listed above) will also be assessed as separate groups, including:

- Medroxyprogesterone
- NOMAC
- CMA

Drug classes and progestogens of interest will be reported by combining WHO ATC codes of interest. Drug classes of interest will be identified using WHO ATC 4th level codes, except for progestogens of interest, which will be identified using WHO ATC 5th level codes. If possible, products containing medroxyprogesterone will be limited to those for non-oncological purposes. A preliminary list of codes can be found in **Appendix I**.

#### 8.6.1. Exposures

Exposures will be considered for patient-level DUS (objective 2 to 5), which consists of individuals with a first-ever prescription of:

- Drug classes of interest and progestogens of interest (objective 3): Progestogens and oestrogens combinations, progestogens that are pregnadien derivates, medroxyprogesterone, NOMAC and CMA.
- NOMAC (objective 2, 4 and 5)
- CMA (objective 2, 4 and 5)

The operational definition of exposures is described by means of **Table 7**. Preliminary concepts for the exposures are detailed in **Appendix I**.

#### 8.6.2 Outcomes

Outcomes will be considered for the population-level DUS (objective 1) and will consist of the 2 drug classes and 3 progestogens of interest described in "8.6 Variables". They will also be considered to study records of drug classes of interest not containing NOMAC nor CMA for objectives aiming to assess line of treatment (objective 4) and switching (objective 5). Meningioma will also be considered as an outcome for Objective 5.

<sup>2 IP = inpatient, OP = outpatient

<sup>3 Specify whether a diagnosis code is required to be in the primary position (main reason for encounter)

P3-	C3-0	106	Study	Protoco	ı

Version: V4.0

Dissemination level: Public

The operational definition of the outcomes is presented in the **Table 8**. Preliminary concepts for the exposures are detailed in **Appendix I**.

Authors: [name], [name], [name], [name], [name] Version: V4.0

Dissemination level: Public

## **Table 7.** Operational definitions of exposure.

Exposure group names 	Details	Washout window	Assessment Window	Care Setting 	Code Type 	Applied to study populations	Incident with respect to
Drug classes of interest (any)	To characterise users of any of the drug classes or progestogens of interest(objective 3). Consisting of first-ever prescription to any of the drug classes or progestogens of interest (see "8.6 Variables").	[-Inf, -1]	0	IP, OP	RxNorm	New users of drug classes or progestogens of interest (objective 3)	Drug classes or progestogens of interest (any)
NOMAC	First-ever prescription to NOMAC. To identify study participants exposed to the drug for objective 2, 4 and 5.	[-Inf, -1]	0	IP, OP	RxNorm	New users of NOMAC (objective 2, 4 and 5)  New users of CMA (objective 2, 4 and 5)	NOMAC
CMA	First-ever prescription to CMA.	[-Inf, -1]	0	IP, OP	RxNorm	New users of NOMAC (objective 2, 4 and 5)  New users of CMA (objective 2, 4 and 5)	CMA

<sup>1 NOMAC = nomegestrol, CMA = chlormadinone

<sup>2 IP = inpatient, OP = outpatient, ED = emergency department, OT = other, n/a = not applicable

<sup>3 RxNorm codes will be identified based on the vocabulary hierarchy, with ATC codes being ancestors.

Authors: [name], [name], [name], [name], [name] Version: V4.0

**Dissemination level:** Public

## Table 8. Operational definitions of outcomes.

Outcome name 	Details	Primary outcome?	Type of outcome	Washout window 	Care Settings 	Code Type⁴	Applied to study populations
Progestogen and estrogen combination products	For incidence/prevalence calculations (Objective 1).	Yes	Count	[-365, -1]	IP, OP	RxNorm	General population (objective 1 and 6)
Progestogens that are pregnadien derivates	For incidence/prevalence calculations (Objective 1).	Yes	Count	[-365, -1]	IP, OP	RxNorm	General population (objective 1 and 6)
Medroxyprogesterone	For incidence/prevalence calculations (Objective 1).	Yes	Count	[-365, -1]	IP, OP	RxNorm	General population (objective 1 and 6)
NOMAC	For incidence/prevalence calculations (Objective 1 and 6).	Yes	Count	[-365, -1]	IP, OP	RxNorm	General population (objective 1 and 6)
СМА	For incidence/prevalence calculations (Objective 1 and 6).	Yes	Count	[-365, -1]	IP, OP	RxNorm	General population (objective 1 and 6)
Progestogen and oestrogen combination products not containing NOMAC or CMA	To assess line of treatment and switches to alternative treatments (Objective 4 and 5).	Yes	Binary	N/A	IP, OP	RxNorm	New users of NOMAC or CMA (objective 2, 4 and 5)
Progestogens that are pregnadien derivates not containing NOMAC or CMA	To assess line of treatment and switches to alternative treatments (Objective 4 and 5).	Yes	Binary	N/A	IP, OP	RxNorm	New users of NOMAC or CMA (objective 2, 4 and 5)
Meningioma	Diagnosis of meningioma	Yes	Binary	[-Inf,-1]	IP, OP	SNOMED	New users of NOMAC or CMA (objective 2, 4 and 5)

<sup>1 NOMAC = nomegestrol, CMA = chlormadinone

<sup>2 For outcomes relative to objective 1 and 6, the washout window will be applied for incidence calculations only.

 $^{3}$  IP = inpatient, OP = outpatient, ED = emergency department, OT = other, n/a = not applicable.

<sup>4 RxNorm codes will be identified based on the vocabulary hierarchy, with ATC codes being ancestors.

